#### Heterogeneity treatment of effect analysis:

For those patients that completed both treatment cycles we will evaluate heterogeneity of treatment effects (HTE) across patients using a linear regression model with UACR response as the outcome. The model includes fixed effects for treatment and subject and a treatment-by-subject interaction, this allows each participant to have a different treatment effect. The statistical significance of patient-level HTE will be assessed by a likelihood test for the interaction term. In addition, we also fit a generalised linear mixed effect (LME) model with a random intercept and slope (for the treatment effect) to estimate the average treatment effect across all subjects. Fixed effects include treatment sequence, and treatment cycle in combination with an unstructured covariance structure.

Also we will use the linear mixed effects model as described above to determine if there is within individual variation in treatment response, we will fit a linear mixed model with correlated random intercepts and random slopes for treatment and include treatment period as a fixed effect. Subsequently, we will compare (using a maximum-likelihood ratio fit test) this model against a random intercept only model with treatment and treatment period as fixed effects.

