### 8.5. Replacement of individual subjects after withdrawal

Patients that meet the inclusion criteria will be invited for participation in the study. When a patient agrees to participate in the study, patients will be invited for screening and informed consent is signed. After the screening visit, eligible patients will proceed to the second visit. When patients decide to withdraw after start of the treatment period, they will be replaced so that twenty patients will complete the full study protocol.

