#### 3.1. General Design and Plan

Subjects with UACR >20 mg/g (2.26 mg/mmol) with a diagnosis of type 2 diabetes who meet the inclusion criteria will be invited for screening. After the screening visit, eligible patients will proceed to the randomization visit. Patients will be randomly assigned to a cross-over study consisting of two periods of 1-week treatment with dapagliflozin and two periods of 1-week treatment with placebo in random order with a 1-week wash-out period between every treatment period to avoid cross-over effects. Based on a prior study, effects of dapagliflozin on UACR, blood pressure, body weight, fasting plasma glucose and eGFR were fully present after 4 days. We will therefore ask patients to collect urine after 3, 5, 6, and 7 days. Due to day-to-day variation in UACR we are collecting multiple urine samples to increase precision and therefore collect urine at 3, 5, 6, and 7 days. We will also collect urine after 1 day to further delineate the time-course of the response to dapagliflozin and assess if the treatment effect on UACR is directly present after 1 day. Blood pressure and body weight will be recorded, and blood samples will be taken at the time points described below and in the table. Overall, a 1-week treatment period is considered sufficient to detect effects on primary and secondary outcomes.

Since data collection will be performed at home using wearable devices and digital technologies, instructions will be provided during the randomization visit to perform data collection and study procedures at home. Data collection and measurements will be performed in each treatment period as indicated in Figure 1. Bottles with smart caps that

Statistical Analysis Plan Page 4 of 13

allow real-time monitoring of adherence, blood pressure monitors, body analysis scales and study medication will be provided at the randomization visit. Patients receive four numbered bottles with seven tablets in each bottle, according to their randomized treatment schema. Patients will be instructed to take the study medication once daily, in the morning.

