#### 5.1. Analysis of primary and secondary study outcome

The change from baseline in UACR will be calculated using the values collected at day 5, 6 and 7 of each treatment and wash-out period. Because of the skewed distribution UACR will be log-transformed before analysis. The geometric mean of these 3 values (at baseline to end of treatment) will be calculated as log(UACRend/UACRbaseline) and the geometric mean change from baseline will be determined.

The study has two cycles of two treatment periods (dapagliflozin and placebo). For the calculation of response, the difference in log-transformed UACR change between dapagliflozin and placebo will be calculated during the first and second cycle. Patient level Bayesian analysis:

First, a Bayesian analysis will be conducted to calculate the posterior probability of dapagliflozin producing a clinically meaningful response on UACR within each individual patient relative to placebo for both treatment cycles combined. Thus for every patient, data of each cycle is combined and expressed in the form of a likelihood function with non-informative priors to calculate the posterior distribution. A clinically meaningful response on UACR is defined as the placebo subtracted percentage UACR change during the first and second cycle with different thresholds of 10%, 20% or 30% reduction in UACR. Population level Bayesian hierarchical analysis:

Subsequently, individual patient results on UACR will be combined to conduct a Bayesian hierarchical analysis to calculate the posterior probabilities of a clinically meaningful response at the population level (10%, 20%, and 30%). Therefore, responses on UACR from each patient will be aggregated into a sample mean and variance, assuming a normal distribution centred around the patient's true mean effect and variance. The Bayesian hierarchical model is defined as:

$$Y_{ij} \sim N(\alpha_i + \beta_i X_{ij}, \sigma_i).$$

Were  $Y_{ij}$  is the placebo subtracted UACR response for the  $i^{th}$  subject at time j and is described by  $x_{ij}$  ( $x_{ij}=1$  if treated with dapagliflozin; =0 if placebo treated). The subject specific intercept and slope were modelled as  $a_i \sim N(a_0, \tau_a^2)$  and  $\beta_i \sim N(\beta_0, \tau_\beta^2)$  respectively. Again, we used non-informative prior for  $a_0$ ,  $\beta_0$ ,  $\tau_a^2$ ,  $\tau_\beta^2$ ,  $\sigma_i$ .

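### The SAP's interaction test of patient-level heterogeneity names no reference distribution; with the default chi-square its false-positive rate would be about 52%, so an F test should be specified.

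*Combined protocol and SAP*

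**What the plan says.** The section of SAP 5.1 on heterogeneity of treatment effect starts: "For those patients that completed both treatment cycles we will evaluate heterogeneity of treatment effects (HTE) across patients using a linear regression model". The model is then described: "The model includes fixed effects for treatment and subject and a treatment-by-subject interaction, this allows each participant to have a different treatment effect". The test is given in one sentence: "The statistical significance of patient-level HTE will be assessed by a likelihood test for the interaction term". No reference distribution, small-sample correction, resampling method or significance level is stated for it.

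The size of the dataset follows from other sections. SAP 3.1 gives each patient "two periods of 1-week treatment with dapagliflozin and two periods of 1-week treatment with placebo in random order". Protocol 8.5 says of patients who withdraw after treatment starts that "they will be replaced so that twenty patients will complete the full study protocol". SAP 5.1 reduces days 5, 6 and 7 to one value per window and expresses response as log(UACRend/UACRbaseline), so there is one value per patient-period.

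The same section plans a second test. A mixed model with random intercepts and random treatment slopes is fitted, and "we will compare (using a maximum-likelihood ratio fit test) this model against a random intercept only model".

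**The concern.** The trial exists to separate real differences in drug response from measurement and day-to-day variation. A significance test of patient-level heterogeneity speaks directly to that aim.

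The chi-square approximation to a likelihood-ratio statistic needs many observations per mean parameter. Here there are two. The maximum-likelihood residual variance divides by 80 although only 40 residual df remain, so it is about half the size it should be and the statistic is inflated. More recruitment does not help, because each further patient adds two mean parameters along with four observations.

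If the analyst takes the software default, the trial could report significant heterogeneity when every patient has the same response. The error favours the hypothesis stated in the protocol's introduction, that the response is a true and reproducible one.

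**Working it through.** **The plan's own figure.** The only design figure is power above 80% for a correlation of 0.6 with 20 patients at alpha 0.05 (SAP 3.2). By Fisher's z, atanh(0.6) × √17 = 0.693 × 4.123 = 2.858. Subtracting 1.960 gives 0.898, and Φ(0.898) = 81.5%. The figure reproduces two-sided. It concerns the correlation between exposures; no error rate is stated for the heterogeneity test.

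**Inputs.**
- Completers: 20 (protocol 8.5).
- Periods per patient: 4 (SAP 3.1), so N = 20 × 4 = 80.
- Outcome: one log ratio per period (SAP 5.1). The regression has a treatment term, so its outcome must be the per-period change, not the placebo-subtracted difference.
- Mean parameters: 20 (subject, including the intercept) + 1 (treatment) + 19 (interaction) = 40.
- Residual df: d = 80 − 40 = 40. Interaction df: q = 19.
- Level: 5%, the conventional value. This is an assumption, since the documents give alpha only for the sample size.

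**Size against chi-square.** For a normal linear model the likelihood-ratio statistic is an exact function of the F statistic:

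LR = N × ln(1 + qF/d) = 80 × ln(1 + 19F/40).

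The 5% critical value of chi-square on 19 df is 30.14. Setting LR equal to it:

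F = (exp(30.14/80) − 1) × 40/19 = 0.4576 × 2.105 = 0.963.

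The test therefore rejects once F exceeds 0.963. With no heterogeneity the mean of F(19, 40) is 40/38 = 1.05, so the cut-off lies below the average null value. The correct 5% point is 1.85.

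False-positive rate = P(F(19, 40) > 0.963) = **51.9%**.

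In 50,000 simulated null trials the chi-square version rejected 52.1% and the F test 4.96%. The mean statistic was 31.8, against the 19 that chi-square assumes. At a nominal 1% level the rate was about 30%. A standard package's likelihood-ratio comparison rejected in 48% of 300 null datasets, which is within simulation error.

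**Sensitivity of the 52%.**

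| Variant | False-positive rate |
|---|---|
| 16 completers | 46% |
| 18 completers | 49% |
| 25 completers | 58% |
| Cycle term added (d = 39) | 54% |
| Four-level period term added (d = 37) | 60% |
| 240 daily rows, days independent | 13% |
| 240 daily rows, assumed within-period correlation 0.1 / 0.3 / 0.5 | 32% / 73% / 93% |

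The daily-row readings depart from the response that SAP 5.1 defines, and the documents give no within-period correlation. Even the best case is well above 5%.

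**How good is the F test?** It is exact only if all patients share one residual variance. The SAP's Bayesian hierarchical model gives each patient a separate σᵢ. With no heterogeneity of effect and an assumed SD of log σᵢ of 0, 0.25, 0.5 and 0.75, the simulated size of the F test was 4.7%, 6.9%, 11.0% and 15.8%.

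**Power of the F test.** If the correlation between cycles is 0.6 and period errors are independent with equal variance, then τ²/(τ² + 2σ²) = 0.6, so τ² = 3σ². The interaction F is then scaled by (τ² + σ²)/σ² = 4, and power is P(F(19, 40) > 1.85/4) = 96%. At a correlation of 0.5 the scale is 3 and power is 87%.

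**The random-slope comparison.** Under the null the slope variance lies on its boundary. The large-sample reference is an equal mixture of chi-square on 1 and 2 df. With the plain chi-square(2) cut-off of 5.99, size = 0.5 × 0.0144 + 0.5 × 0.05 = 3.2%.

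**The case against.** The strongest reply is that the SAP never mentions chi-square. In a normal linear model the likelihood ratio is a monotone function of F, so an analyst who refers it to F(19, 40) follows the SAP's words and holds 5% under equal variances. This stands. A reader might infer that the SAP as written has a 52% false-positive rate; the documents do not support that. The 52% belongs to the default chi-square reference, which the text leaves open and does nothing to rule out.

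A reader might also infer that this test alone settles the trial's central question. It does not:
- The SAP puts the patient-level and hierarchical Bayesian analyses first, and the hierarchical model estimates the between-patient slope variance directly.
- The sample size rests on the correlation between exposures, which is analysed separately.
- Protocol 10.1 has the correlation and the random-slope comparison but no fixed treatment-by-subject test.
- No treatment decision or stopping rule depends on this p-value.

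These facts limit the consequence of a false positive but do not make the test sound. The Bayesian analyses, as planned, report probabilities of passing response thresholds and not a test of whether patients differ.

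Finally, the 52% does not carry over to the random-slope comparison, which does not have 40 mean parameters and errs in the conservative direction. The two tests address one question and could disagree, and the SAP has no rule for that case.

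**Conclusion.** The concern holds as a specification gap with a large consequence under the default reading. The false-positive rate is 51.9% with 20 completers and the model as written, and 59.5% with a four-level period term.

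The result assumes the usual maximum-likelihood ratio statistic against chi-square(19), a 5% level, one log(UACRend/UACRbaseline) per period, and independent normal errors with equal variance. Moderate changes in the number of completers leave it between 46% and 58%.

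The F test removes nearly all of the problem, but it is approximate if residual variance differs between patients (about 7% to 16% for the assumed spreads above). The random-slope point is minor and separate: about 3.2% against a nominal 5%, a large-sample figure that may not be accurate with 20 patients.

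**What to change.** 1. Keep the SAP's response, one log(UACRend/UACRbaseline) per patient-period. Replace the likelihood test with the F test of the treatment-by-subject interaction on (19, 40) df, or (19, 37) if a four-level period term is included. For n completers these are (n − 1, 2n) and (n − 1, 2n − 3). State the significance level.
2. Add a permutation or heteroscedastic bootstrap p-value for the same interaction as a sensitivity check, because the SAP's hierarchical model allows patient-specific residual SDs. Treat it as a check, since with four values per patient no such method is exact.
3. For the random-slope versus random-intercept comparison, use the 50:50 mixture of chi-square on 1 and 2 df, or a parametric bootstrap.
4. Say which of the two heterogeneity tests leads if they disagree.

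The cost is a few sentences in SAP 5.1 and some programming for the resampling. It needs no new data or patients. At the design correlation of 0.6 the F test keeps about 96% power under the stated assumptions. The change should be made before the data are unblinded.

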However, it should be noted that randomized parallel group placebo controlled clinical trials are used to test the efficacy and safety of new interventions on a population level but do not assess the efficacy of a drug for the individual. Thus, although analyses from parallel group trials have shown variation between patients in response in UACR or blood pressure to dapagliflozin, it cannot be excluded that this variation is due to measurement or temporal random variation. Alternative trial designs are needed and better suited to evaluate the individual response to dapagliflozin. Various clinical trial designs have been developed that better account for the variability between patients than the traditional randomized parallel group double blind controlled trial. The N=1 clinical trial design specifically allows for assessment of drug efficacy and safety at an individual level. In a N=1 trial, the same patient is exposed multiple times in random order to an active compound or placebo intervention in order to directly estimate the effect of the intervention for each individual. The advantage of a N=1 trial is that the efficacy of the intervention is vetted for the actual patient, thereby increasing patient participation and engagement and making the results of the study directly applicable to the participant. Thus, categorizing patients as responders or non-responders by comparing their values with those at baseline is arbitrary and inefficient since the observed change does not guarantee that the patient is responding to the drug. A N=1 trial with the same patient exposed twice to active medication and placebo is the appropriate design to test the individual drug response.

We therefore propose a N=1 trial determining the UACR response to dapagliflozin for each individual specifically. We furthermore hypothesize that the change in UACR in response to dapagliflozin is reproducible upon re-exposure and reflects a true pharmacological response rather than random variation whereas during placebo treatment changes in UACR are thought and do not correlate. A retrospective analysis

from a cross-over study in non-diabetic kidney disease where patients were exposed twice to an ACE inhibitor or Angiotensin Receptor Blocker supports this notion as in that study a strong correlation between the response during the first and second exposure was observed (correlation coefficient between 0.7 and 0.9).

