#### 10. STATISTICAL ANALYSIS

#### 10.1. Primary study parameter(s)

The change from baseline in UACR will be calculated using the values collected at day 5, 6 and 7 of each treatment and wash-out period. Because of the skewed distribution UACR will be log-transformed before analysis. The geometric mean of these 3 values (at baseline to end of treatment) will be calculated as log(UACRend/UACRbaseline) and the geometric mean change from baseline will be determined.

The study has two cycles for two treatment periods (dapagliflozin and placebo). For calculation of response, the difference in UACR change between dapagliflozin and placebo will be calculated during the first and second cycle. To this end a linear mixed effects model with random intercepts and random slopes for treatment will be used to determine the response during each period. Fixed effects include treatment sequence, and treatment cycle. Baseline log transformed UACR may be added as covariate. Appropriate contrasts will be implemented to assess the placebo substracted response during the first and second cycle and to correlate the placebo adjusted UACR responses to dapagliflozin (fitted on the log-scale) during the two treatment periods. The variance-covariance pattern of the mixed effects model is assumed to be unstructured. If the model does not converge less stringent models will be considered.

To determine if there is within individual variation in treatment response, we will fit a linear mixed model with correlated random intercepts and random slopes for treatment and include treatment period as a fixed effect. Subsequently, we will compare (using a maximum-likelihood ratio fit test) this model against a random intercept only model with treatment and treatment period as fixed effects.

In an additional supportive analysis, we will also dichotomize response. If the placebo adjusted difference in both cycles is greater than 20% in favor of dapagliflozin (using the linear mixed effects model), the patient will meet the response definition. We will then perform a McNemar test for the proportion of concordant response (response during the two cycles or no response during

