#### 3.2. Sample Size

The sample size for this study is based on the hypothesis that the response to dapagliflozin is reproducible upon re-exposure and thus correlates between the first and second exposure while no correlation will be detected during placebo patients. A prior retrospective study found that during intervention in the renin-angiotensin-system responses in proteinuria correlate with correlation coefficients ranging between 0.7 to 0.9. Since this was a retrospective study, we assume a more conservative correlation coefficient of 0.6. A sample size of 20 patients provides >80% power (alpha 0.05) to detect a correlation coefficient of 0.6.

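### The random-slope likelihood-ratio test states no residual variance per treatment, so on the default reading it cannot tell stable patient differences in response from a drug effect that fluctuates between exposures

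*Combined protocol and SAP*

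**What the plan says.** Each patient receives "two periods of 1-week treatment with dapagliflozin and two periods of 1-week treatment with placebo in random order" (SAP 3.1), arranged as two cycles with one week of each treatment. SAP 5.1 reduces each period to one log change in UACR, from the day 5, 6 and 7 values. A completer therefore contributes four values. Under protocol 8.5, patients who withdraw after treatment starts are replaced: "they will be replaced so that twenty patients will complete the full study protocol". That gives 20 x 4 = 80 values.

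The test in question stands at the end of the heterogeneity part of SAP 5.1: "we will fit a linear mixed model with correlated random intercepts and random slopes for treatment and include treatment period as a fixed effect". The analysts will then "compare (using a maximum-likelihood ratio fit test) this model against a random intercept only model". Protocol 10.1 plans the same test: "we will fit a linear mixed model with correlated random intercepts and random slopes for treatment".

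Three things are left open:
- **Residual variance.** Nothing says whether it is common to all weeks or separate by treatment. The term unstructured appears for the mixed models in SAP 5.1, but it is not tied to the random effects or to the residuals.
- **Reference distribution and alpha** of this test.
- **Fixed effects.** Treatment is named as a fixed effect only for the smaller model.

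Protocol section 1 states the aim: to show that the response is "reproducible upon re-exposure and reflects a true pharmacological response rather than random variation".

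**The concern.** A patient's drug effect can differ from the average in two ways. It can differ in the same direction at both exposures, which is a stable patient difference. Or it can differ from one exposure to the next with no pattern. Only the first is a reproducible response. Both widen the spread of dapagliflozin weeks relative to placebo weeks.

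If both models carry a single residual variance, the larger model can fit that wider spread only through its slope variance and covariance. A significant likelihood ratio would then be reported as true variation between patients even if no patient responded more consistently than another. What is at stake is the heterogeneity claim, not the estimate of the average effect.

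**Working it through.** **1. The plan's own figure.** SAP 3.2 says: "A sample size of 20 patients provides >80% power (alpha 0.05) to detect a correlation coefficient of 0.6". Fisher z, two-sided: power = Phi(atanh(0.6) x sqrt(20 - 3) - 1.960) = Phi(0.6931 x 4.1231 - 1.960) = Phi(0.898) = 81.5%. The figure reproduces. It concerns the correlation between exposures, not the random-slope test, for which no power or error rate is given.

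**2. Why one residual variance mixes the two sources.** Let P and D be placebo and dapagliflozin weeks of one patient. Let A be the intercept variance, B the slope variance, C their covariance and s2 the residual variance.

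| Quantity | Model with one residual variance | Truth with no slope, D noise = k x P noise |
|---|---|---|
| Var(P) | A + s2 | A + s2 |
| Var(D) | A + 2C + B + s2 | A + k s2 |
| Cov(P, P') | A | A |
| Cov(D, D') | A + 2C + B | A |
| Cov(P, D) | A + C | A |

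The model forces Var(D) - Var(P) to equal Cov(D, D') - Cov(P, P'). In truth the first is (k - 1) s2 and the second is 0. The fit compromises, and part of (k - 1) s2 goes into the slope terms. With residual variances sP2 and sD2 there are five parameters for these five quantities, so the slope is identified by the covariances alone. Two weeks per treatment are enough.

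Reading unstructured as a residual matrix does not help. A 4 x 4 unstructured matrix has 10 free terms and already saturates four values per patient, so a random slope on top is not identifiable. It would also follow period rather than treatment.

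**3. Size.** Simulation settings:
- 20 patients, sequences DPDP, DPPD, PDDP and PDPD, true slope variance 0
- treatment and period fixed in both models, ML fits, one residual variance
- 2,000 trials per cell, nominal 5%

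Each cell gives rejections against chi-square with 2 df / against a 50:50 mixture of 1 and 2 df. Intercept variance is in units of placebo noise variance.

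| Ratio k | Intercept 0 | 0.5 | 1 | 2 |
|---|---|---|---|---|
| 1 | 2.8 / 3.7% | 2.7 / 4.2% | 3.0 / 4.8% | 3.6 / 5.7% |
| 1.5 | 5.2 / 7.1% | 3.6 / 5.6% | 3.4 / 4.9% | 4.5 / 6.5% |
| 2 | 9.7 / 12.5% | 7.3 / 10.0% | 5.7 / 9.1% | 5.9 / 8.3% |
| 2.5 | 14.8 / 19.8% | 12.2 / 16.7% | 7.7 / 11.7% | 6.1 / 9.1% |
| 3 | 21.6 / 27.1% | 16.7 / 21.3% | 13.5 / 17.0% | 9.7 / 12.8% |
| 4 | 30.8 / 36.9% | 26.5 / 31.9% | 20.9 / 26.7% | 13.4 / 17.8% |

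Monte Carlo error is at most about 1.96 x sqrt(0.3 x 0.7 / 2000) = 2 points around a rate of 30%. Across several separately coded simulations and both references, the zero-intercept rates are about 2-4% at k = 1, 8-15% at 2, 14-23% at 2.5 and 28-37% at 4. At k = 2.5 with intercept variance equal to placebo noise they are about 8-15%. Quieter dapagliflozin weeks also inflate the rate: about 9-13% at k = 0.5 with zero intercept variance.

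**4. Which ratios are conceivable.** The documents give no noise figure for either kind of week. One bounding case uses the planned correlation of 0.6 and supposes that the whole share planned as reproducible is fluctuation between exposures instead.
- If 0.6 refers to placebo-subtracted responses: 2 s2 + v = 1 and v = 0.6, so s2 = 0.2 and k = (0.2 + 0.6) / 0.2 = 4.
- If it refers to unsubtracted dapagliflozin-week changes: s2 + v = 1 and v = 0.6, so s2 = 0.4 and k = 1 / 0.4 = 2.5 (zero intercept variance).

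These are assumed extremes, not expected values.

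**5. Separate residual variances in both models.** At k = 4 the false-positive rate (2 df) is 1.9%, 2.8%, 2.9% and 3.0% for intercept variance 0, 0.5, 1 and 2. In another run with zero intercept variance, it stays at 2.0-3.7% for ratios from 0.5 to 4 under both references.

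**6. Other analyses.** An exact F test of the treatment-by-patient interaction rejects in about 4-7% of trials in these scenarios. Independent exposures also imply no correlation between the placebo-subtracted responses of the two cycles.

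**The case against.** The strongest reply is that the alternative explanation the protocol names is measurement or temporal random variation. Noise of that kind affects placebo and dapagliflozin weeks alike, so the ratio is 1 and the test holds its level. This stands. A reader might infer that a non-reproducible response makes dapagliflozin weeks noisier by definition. It does not: a constant drug effect plus ordinary noise also gives uncorrelated responses, with no extra variance. The failure needs a drug effect that itself fluctuates, which the documents neither raise nor quantify.

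A reader might also take about 23% as the worst case. It is neither a ceiling nor derivable from the documents. It needs an assumed ratio of 2.5, the mixture reference and zero intercept variance. Higher ratios give more, and higher intercept variance gives less. The outcome is a change from baseline, which removes much of a patient's stable level and argues for low intercept variance, but no figure is given.

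Nor does the plan state that noise is equal; that is inferred from silence.

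Finally, this test is not the trial's only verdict. The study is sized on the between-cycle correlation, the SAP puts the Bayesian analyses first, and both documents describe this test's purpose as variation within individuals. All true, although a random slope measures variation between patients, so a positive result would naturally be read that way. The interaction analysis is not a secure backstop as written: SAP 5.1 plans a likelihood test, not an exact F test. Against chi-square with 19 df, that likelihood ratio rejects in about half of simulated trials even with equal noise.

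**Conclusion.** The point holds as a conditional weakness. On the default reading, the random-slope test cannot separate stable patient differences from a drug effect that varies between exposures of the same patient. Its false-positive rate is acceptable if noise is equal. With zero intercept variance it rises to about 14-23% at an assumed ratio of 2.5 and 28-37% at 4, and less with larger intercept variance. The conclusion rests on one common residual variance, identical fixed effects in both models, 20 completers with four values each, and an unknown variance ratio. The documents do not support saying that the test will mislead, only that the plan does not protect against it. The between-cycle correlation and an exact F test of the interaction are not affected in the same way.

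**What to change.** In SAP 5.1 and protocol 10.1:
- State the residual structure, the fixed effects (identical in both models) and the reference distribution of the test.
- Add the same comparison with a separate residual variance for dapagliflozin and placebo periods in both models.
- Report the slope SD with its 95% CI, and both residual variances.
- Do not claim true between-patient variation from the equal-variance test unless the separate-variance comparison supports it.

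The planned model can stay alongside. Replacing it outright is debatable because of the power cost when noise is in fact equal. With low intercept variance, power falls from about 99% to 95-97% at a between-cycle correlation of 0.6. With intercept variance equal to placebo noise, it falls from 95% to 92% (2 df). At a correlation of 0.43, an assumed value, it falls from about 89% to 74-77%. Otherwise the cost is one extra variance parameter and a few lines of text, with no new data.

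### As written, the likelihood-ratio test for response heterogeneity compares models that are not nested, because treatment is a listed fixed effect only in the smaller one

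*Combined protocol and SAP*

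**What the plan says.** The last paragraph of the heterogeneity analysis in SAP 5.1 defines two models. The larger is a "linear mixed model with correlated random intercepts and random slopes for treatment and include treatment period as a fixed effect". The SAP then compares "this model against a random intercept only model with treatment and treatment period as fixed effects". Protocol 10.1 gives the same pair: "Subsequently, we will compare (using a maximum-likelihood ratio fit test) this model against a random intercept only model". Both documents describe the target as variation in response within individuals.

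The SAP introduces the larger model with "Also we will use the linear mixed effects model as described above". The model above it is a random intercept and slope model meant "to estimate the average treatment effect across all subjects", but its listed terms are: "Fixed effects include treatment sequence, and treatment cycle in combination with an unstructured covariance structure". The response model in the SAP's frequentist section and in protocol 10.1 also lists only sequence and cycle, with baseline UACR as an optional covariate.

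The same SAP paragraph block first gives a separate heterogeneity test by linear regression: "The model includes fixed effects for treatment and subject and a treatment-by-subject interaction".

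**The concern.** A likelihood-ratio test with a chi-square-type reference needs the smaller model to be a special case of the larger. Here, setting the slope variance to zero in the larger model gives a model with no treatment effect at all, which is not the comparator. The larger model gains a slope variance but loses the mean effect. It must treat a shift shared by all patients as if it were spread around zero. The better dapagliflozin works on average, the worse this model fits relative to the comparator, whatever the true heterogeneity.

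The purpose of the trial is to separate true differences in response from random variation. A test that reads a strong average effect as evidence against heterogeneity could give a false negative on that question. A positive result would be described as variation within individuals, although a random treatment slope measures variation between patients.

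**Working it through.** **Inputs from the documents.** 20 completers (protocol 8.5). Two dapagliflozin and two placebo periods each (SAP 3.1). Planning correlation between cycles 0.6, alpha 0.05 (protocol 4.4, SAP 3.2). Mean effect: the prior trial's 36.2% reduction in 24-hour albumin excretion (protocol 6.3), μ = ln(1 − 0.362) = −0.449.

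**The plan's own figure.** Fisher z: Φ(atanh(0.6) × √17 − 1.96) = Φ(0.693 × 4.123 − 1.96) = Φ(0.898) = 81.5%. The stated power above 80% is reproduced, two-sided.

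**Assumed, because the documents give no value.** Slope SD τ from 0.15 to 0.5 on the log scale. Residual SD σ set so that the between-cycle correlation τ²/(τ² + 2σ²) equals 0.6, that is σ = τ√(0.4/1.2). Intercept SD 0.2 in the table.

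**Why the statistic goes negative.** A patient's mean dapagliflozin-minus-placebo difference has variance v = τ² + σ². Fixing the mean slope at zero inflates the fitted variance to about v + μ². So, approximately,

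LR as written ≈ LR nested − N ln(1 + μ²/v).

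With N = 20 and μ² = 0.2016:
- τ = 0.2, v = 0.0533: 20 ln(4.78) = 31.3
- τ = 0.3, v = 0.12: 20 ln(2.68) = 19.7
- τ = 0.4, v = 0.2133: 20 ln(1.945) = 13.3

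The simulated mean nested LR at these settings is 17.2, 19.6 and 21.7. The as-written means are −16.3, −2.0 and 6.8, so the simulated gaps are 33.5, 21.6 and 14.9, close to the formula.

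**Simulated power.** Maximum-likelihood fits, 20 patients × 4 periods, balanced sequences, period fixed effects, 400 runs per row, chi-square with 2 df at 0.05:

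| Slope SD | Residual SD | Nested | As written | LR negative |
|---|---|---|---|---|
| 0.15 | 0.087 | 91.2% | 0.3% | 97.5% |
| 0.20 | 0.115 | 92.2% | 6.8% | 86.8% |
| 0.25 | 0.144 | 94.3% | 16.0% | 72.8% |
| 0.30 | 0.173 | 94.5% | 26.8% | 57.5% |
| 0.40 | 0.231 | 96.0% | 50.2% | 32.5% |
| 0.50 | 0.289 | 97.3% | 67.2% | 17.5% |

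A second, separate simulation at correlation 0.6 gave about 1%, 12% and 38% as written at slope SD 0.2, 0.3 and 0.4, with 84-90% nested. The intercept SD matters: refitting with 0.9 in place of 0.2 lowers nested power and, at slope SD 0.3 and 0.4, clearly lowers as-written power.

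**Sensitivity**, with slope SD 0.15 to 0.5 in the first two lines and 0.2 to 0.4 in the rest:
- Correlation 0.4: 0-35% as written, 53-77% nested.
- Correlation 0.8: 19-95% as written, above 99% nested.
- Correlation 0.6, mean reduction 20%: 32-73% as written.
- Correlation 0.6, mean reduction 10%: 65-87% as written.
- Correlation 0.6, no mean effect: 87-90% as written, 90-93% nested.

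**No heterogeneity** (σ = 0.2). At μ = −0.449 the as-written test rejected in 0 of 500 runs and the LR was negative in all of them. The nested test rejected in 3.8%, so chi-square with 2 df is mildly conservative. The 50:50 mixture of chi-square with 1 and 2 df has a 5% cut-off of 5.14, against −2 ln(0.05) = 5.99 for 2 df.

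**The case against.** The strongest defence is that treatment was left out by oversight. The larger model is tied to one meant to estimate an average treatment effect, the response model calls for placebo-subtracted contrasts, and a list introduced by the word include need not be complete. This stands as a reading of intent: the text omits the term rather than ruling it out. It does not settle the specification. The model referred to lists only sequence and cycle, while the comparator in the adjacent sentence names treatment explicitly. Treatment period cannot stand in for treatment, because the comparator lists the two separately. A programmer following the text would fit the wrong pair.

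A second defence is the separate treatment-by-subject interaction test, which is properly nested. As an F test it has about 96% power at correlation 0.6, so detection does not rest on the mixed-model test alone. But the SAP names a likelihood test. With 80 period-level responses and 40 residual df, the LR is 80 ln(1 + 19F/40). It passes the chi-square(19) cut-off of 30.14 when F > (40/19)(e^(30.14/80) − 1) = 0.963, which happens about 52% of the time with no heterogeneity. Referred to that distribution, it is not a safe substitute.

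A reader might infer that the test almost never detects heterogeneity. The documents do not support that. With slope and residual SD both 0.3 (correlation 0.09/(0.09 + 0.18) = 0.33), power is about 2.5% as written against 36% nested. But those SDs are assumed and sit below the planning correlation, and the test recovers as heterogeneity grows relative to the mean effect. A reader might also infer that the trial does not estimate an average effect. The SAP's Bayesian hierarchical model does, through its population mean slope. The gap is confined to the frequentist mixed model.

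On the label, the SAP paragraph opens by naming heterogeneity across patients, so the later description is a wording error within a correctly stated aim.

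**Conclusion.** The point holds. In both documents the two models are not nested as written, and the likelihood-ratio statistic has no valid chi-square reference. With a 36.2% mean reduction and a between-cycle correlation of 0.6, power falls from roughly 85-97% to under about 10% at slope SD 0.2 or less, about 10-30% at 0.3 and about 40-50% at 0.4. These figures rest on assumed slope, residual and intercept SDs. Power is near zero only when the mean effect is about twice the slope SD or more, and the loss is minor when the mean effect is small. The frequentist model for the average effect has the same omission, and the target is mislabelled. The choice of reference distribution after nesting is a refinement. The SAP puts the Bayesian analyses first and the sample size rests on the correlation, which limits the harm. Even so, the test addresses the trial's central question and should be corrected before the data are analysed.

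**What to change.** In protocol 10.1 and in the frequentist and heterogeneity parts of SAP 5.1:

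- List treatment as a fixed effect in every mixed model.
- Define the heterogeneity test as random intercept plus treatment slope against random intercept only, both with the same treatment and period fixed effects and both fitted by maximum likelihood.
- State the reference distribution: the 50:50 mixture of chi-square with 1 and 2 df, or a parametric bootstrap. Plain chi-square with 2 df is acceptable if its mild conservatism is noted.
- Name the target as between-patient variation in treatment response.

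The cost is a change of wording in the two documents. No extra data, patients or visits are needed.
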